5.1.2 Protein and RNA Analysis

In addition, protein analysis of plasma and urine will be conducted to explore if markers of senescence can predict for the risk of normal tissue injury after radiation. [name] laboratory has extensively studied normal tissue injury as a consequence of stem cell senescence or as a consequence of elaboration of molecules associated with senescence [42, 43, 62-66]. A number of these molecules known to be secreted after senescence, known as the senescence associated secretory phenotype (SASP)[67], will be evaluated with multiplex ELISA or similar quantitative protein assays in plasma and urine. Finally, plasma samples may be used to purify exosomes for further analysis via flow cytometry, protein assays, or RNA based approaches. These studies are all exploratory.

5.1.3 Samples

5.1.3.1 Plasma

Plasma will be sampled at baseline (within 2 weeks prior to radiation), at the end of radiation, 1 month after radiation, and every three months after radiation until 24 months.

Two 8 mL aliquots of blood will be obtained in EDTA containing tubes ([name]/[name]) and one aliquot of whole blood in a STREK tube. CEC/CEP analysis will only occur at selected time points. For CEC/CEP and immune subset analysis, whole blood will be collected in two 8 mL

BD Vacutainer Cell Preparation Tubes (CPT/citrate) aliquots will be collected in citrate CPT tubes. CEC/CEP collections will occur prior to treatment (baseline, the last day of treatment, one month after treatment, and at one optional blood draw at a later follow up appointment. Following collection, EDTA tubes will be immediately placed on ice and transferred to the laboratory of [name] for processing and storage, [name], [contact].

Samples for DTB Clinical Translational Unit (CPT tubes): Please notify the lab by email ([name] - [contact]; [name] - [contact] and [name] - [contact]) that the blood draw has been scheduled. When the blood is being drawn, please call the Lab at [contact] to arrange for immediate pick- up.

Plasma will be stored and batched for analysis.

Plasma assays in [name] laboratory will include ELISA/Bioplex analysis of predictive biomarkers recently identified by the [name] laboratory that correlate with tumor resistance to radiotherapy (70 analytes) or toxicity. Studies in [name] laboratory will include surface receptor analysis by nanoFACS and RNAseq, for exosome and extracellular RNA analysis.

5.1.3.2 Urine

Urine will be sampled at baseline and every three months after SBRT.

At least 15 mL of urine will be obtained in a sterile collection cup. Following collection, urine will be transferred to the laboratory of [name] for processing, measurement of creatinine concentration, and storage.

Urine will be stored and batched for analysis.

Urine assays will include ELISA analysis of predictive biomarkers recently identified by the [name] laboratory that correlate with tumor resistance to radiotherapy (70 analytes identified in tissue, screening for detection will occur in urine and plasma).

5.1.4 MRI of erectile tissue

The erectile tissue lies just beneath the prostate. After prostatectomy, the penile bulb (base of the corpus cavernosa and spongiosa) is used as a landmark for the inferior portion of the radiation target volume. Patients treated with radiation to the prostate on 13-C-0119 have undergone pre-treatment and post-treatment MRI for evaluation of treatment response. On interesting component of this analysis has been the finding that erectile tissue shrinks substantially in patients treated with radiation and ADT. Because a treatment planning MRI is often obtained (as per standard) we have noted a major change in the erectile tissue from baseline until the time of radiation, corresponding to two months of treatment with ADT. Less change is found after the addition of radiation. Thus, much of the change observed in the erectile tissue may be due to ADT. We hope to expand these observations in an exploratory fashion to the post-prostatectomy setting. In this case, we plan to evaluate the width and imaging characteristics of erectile tissue at baseline and 6 months after treatment. The percent reduction in width of the erectile tissue and the volume of the penile bulb will be evaluated at 6 months after treatment. Changes in the imaging characteristics of erectile tissue in patients treated with ADT and without ADT will be evaluated separately.

5.2 SAMPLE STORAGE, TRACKING AND DISPOSITION

Samples will be ordered in CRIS and tracked through a Clinical Trial Data Management

Abbreviated Title: Image guided radiation

Version Date: 06/03/2024

system. Should a CRIS screen not be available, the CRIS downtime procedures will be followed. Samples will not be sent outside NIH without appropriate approvals and/or agreements, if required.

All samples collected on this protocol and stored in [name] or [name] laboratories will be labelled and catalogued with LabMatrix. Labmatrix access within the laboratories is restricted to laboratory members processing and storing specimens.

Samples to be analysed in [name] and [name] laboratory will be immediately processed and stored at -80° C until use in the ROB clinical specimen freezers.

Samples to be analysed by [name] are processed appropriately and stored in secure freezers at -80° C until use.

Samples stored in the DTB Clinical Translational Unit laboratory will be immediately processed. Specimens are stored in secure freezers at optimal temperatures for the sample type, i.e. -80° for plasma and liquid nitrogen for viably frozen cells. All freezers are continually monitored. Samples are 2D barcoded without identifying information. Access to the patient database and code key is limited to defined laboratory personnel, and access is only possible on limited computers with a password-restricted login.

All specimens obtained in the protocol are used as defined in the protocol. Any specimens that are remaining at the completion of the protocol will be stored in the conditions described above. The study will remain open so long as sample or data analysis continues. Samples from consenting subjects will be stored until they are no longer of scientific value or if a subject withdraws consent for their continued use, at which time they will be destroyed. The PI will record any loss or unanticipated destruction of samples as a deviation. Reporting will be per the requirements of section [7.2](#).

Blood and urine samples may be subjected to protein or RNA analysis in the future to describe novel prognostic or predictive biomarkers.

If the patient withdraws consent the participant's data will be excluded from future distributions, but data that have already been distributed for approved research use will not be able to be retrieved.

5.3 SAMPLES FOR GENETIC/GENOMIC ANALYSIS

5.3.1 Description of the scope of genetic/genomic analysis

5.3.1.1 Tumor whole genome sequencing

If available, tissue blocks or sections from prostatectomy or biopsies will be requested to perform whole genome sequencing or RNA analyses. This data will be used for comparison to circulating DNA analyses as outlined below or as a compliment to exosome studies. These will be exploratory analyse to compare the circulating DNA copy number results or exosome analyses to previously resected tumour tissue. These analyses may only be carried out if circulating DNA analyses or exosome analyses are promising as defined below.

5.3.1.2 Circulating DNA

The anticipated analysis on circulating DNA will include whole genome sequencing with copy number analysis, performed by [name] laboratory.

We will use the approach of whole genome sequencing with copy number analysis of circulating cell free DNA. Copy numbers that vary from expected at baseline will be used as a tumor marker in longitudinal sample assessment (copy number abnormality at baseline will be compared to a reference region at follow up time points). This is purely an exploratory analysis to determine feasibility of the approach.

5.3.2 Description of how privacy and confidentiality of medical information/biological specimens will be maximized

- Samples will be bar coded for storage and personal identifiers will be removed. Names and demographic data will be linked to bar codes in the password protected LabMatrix database. This data will be accessible only by the PI and the research nurses within the ROB.
- Samples provided to CCR collaborators will be barcoded. No personally identifiable information will be released to [name].
- Data from genomic and genetic data will be deposited in dbGAP and released in accordance with NIH guidelines.
- As part of study efforts to provide confidentiality of subject information, this study will obtain a Certificate of Confidentiality. Please refer to Section **10.4**.

5.3.3 Management of Results

We plan to contact participants if a clinically actionable gene variant is discovered. Clinically actionable findings for the purpose of this study are defined as disorders appearing in the American College of Medical Genetics and Genomics recommendations for the return of secondary findings that is current at the time of primary analysis. (A list of current guidelines is maintained on the CCR intranet:

<https://ccrod.cancer.gov/confluence/display/CCRCRO/Incidental+Findings+Lists>). Unless requested otherwise, participants will be contacted at this time with a request to provide a sample to be sent to a CLIA certified laboratory.

5.3.4 Genetic counseling

If the research findings are verified in the CLIA certified lab, the participant will be offered the opportunity to schedule a visit, in person (at our expense) or via telemedicine on an NIH approved platform to have genetic education and counseling with the NCI Genetics Branch to explain this result. If the subject does not want to come to NIH, a referral to a local genetic healthcare provider will be provided (at participant's expense).

This is the only time during the course of the study that secondary findings will be returned. No interrogations regarding clinically actionable findings will be made after the primary analysis.

Participants will be requested to maintain up to date contact information to enable future contact.

6 DATA COLLECTION AND EVALUATION

6.1 DATA COLLECTION

The PI will be responsible for overseeing entry of data into a 21 CFR Part 11-compliant data capture system provided by the NCI CCR and ensuring data accuracy, consistency and timeliness. The principal investigator, associate investigators/research nurses and/or a contracted

Abbreviated Title: Image guided radiation

Version Date: 06/03/2024

data manager will assist with the data management efforts. Primary and final analyzed data will have identifiers so that research data can be attributed to an individual human subject participant.

All adverse events, including clinically significant abnormal findings on laboratory evaluations, regardless of severity, will be followed until return to baseline or stabilization of event. Document AEs from the first study intervention through at least 30 days after the last study treatment administration. Beyond 30 days after the last study treatment administration, only adverse events which are serious and related to the study intervention need to be recorded.

An abnormal laboratory value will be considered an AE if the laboratory abnormality is characterized by any of the following:

- Results in discontinuation from the study (except for a rising serum PSA)
- Is associated with clinical signs or symptoms
- Requires treatment or any other therapeutic intervention
- Is associated with death or another serious adverse event, including hospitalization.
- Is judged by the Investigator to be of significant clinical impact
- If any abnormal laboratory result is considered clinically significant, the investigator will provide details about the action taken with respect to the test drug and about the patient's outcome.

End of study procedures: Data will be stored according to HHS, FDA regulations, and NIH Intramural Records Retention Schedule as applicable.

Loss or destruction of data: Should we become aware that a major breach in our plan to protect subject confidentiality and trial data has occurred, this will be reported expeditiously per requirements in section [7.2.1](#).

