3.1.1 Dose Limiting Toxicity

The DLT period includes treatment period (4, 3 or 2 weeks depending on Dose Level) and the 3 following weeks. DLT is defined as any of the following:

- Grade 3 rectal, small bowel, or urinary toxicity that does not resolve to Grade 2 or less within 4 days with appropriate medical management.
- Other grade 3 in-field toxicities attributable to RT that do not resolve to Grade 2 or less within 4 days with medical management.
- Delays of more than one week in completing radiation treatment due to toxicity (cumulative duration of delay over the course of the entire treatment).

Additionally, toxicities that occur more than 3 weeks after completion of treatment and during the 24 month follow up period will be followed and scored but will not be used for escalation with the following exception. If Grade ≥ 4 late bowel or bladder injury is observed in 2 patients at any Dose level, dose escalation will be terminated and the dose below that dose level in which the toxicity was observed will be considered the MTD. Early and late toxicities used for assessment of DLTs should be attributable (possible, probable or definite) to radiation. Changes in sexual and erectile function will not be considered a DLT. MTD will be determined for each Arm separately.

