3.3 STUDY CALENDAR

Procedure	Screening	Baseline ¹	Active RT treatment (2-4 weeks)	Follow Up, Months ⁷		
				1	3	6, 9, 12, 15, 18, 21, 24
RT treatment			X			
Medical History/Records	X					
Confirmation of Pathology	X					
Physical exam, vital signs, ECOG	X	X		X		
CBC with differential and platelet count		X				
Biochemical profile ²		X				
PSA	X	X			X	X ⁵
Testosterone		X			X	X ⁵
HIV	X					
CD4+ T-cell count for HIV positive patients	X					
Lymphocyte phenotype TBNK		X		X	X	X
Adverse Events		X	X	X	X	X
Concomitant Medications		X	X	X	X	X
mpMRI	X					X ⁸
Whole body bone scan or 18F-NaF PET/CT imaging ⁹	X					
CT of the abdomen and pelvis (if clinically indicated)	X					
Blood for correlative studies		X	X ³	X	X	X ⁵
Urine for correlative studies		X	X ³	X	X	X ⁵
Questionnaires ⁶		X				X ⁴
Archival tissue (if available, blocks or sections from prostatectomy or biopsies will be requested)		X				
Contact by phone call, e-mail or other NIH approved remote communication platform every 3 months once off treatment and unable to return for visits				X	X	X

1. Tests done at screening do not need to be repeated on baseline if performed in designated time frame prior to start of treatment
2. Biochemical profile: electrolytes, creatinine, BUN, alkaline phosphatase, ALT, AST, total and direct bilirubin
3. Sampling within 24 hours after the last dose of irradiation.
4. Every 6 months after treatment for 24 months
5. Every 3 months after radiation treatment for 24 months
6. Questionnaires: Expanded Prostate Cancer Index Composite (EPIC-26), SHIM, AUA-SI, PROMIS Depression SF4a, PROMIS Anxiety SF4a, PROMIS Psychological Impact Positive SF 4a, Decision Regret Scale. If the patient receives ADT, before initiation of ADT and within one week before starting radiation if ADT initiated more than one month prior to radiation. For English speaking patients only.

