6.1.1 Data Elements/Information

The presence of any pre-administration event (baseline signs and symptoms present just before radiation) will be recorded in the clinical research database:

- The date and time of evaluation
- The onset time
- The resolution time or duration
- Action taken
- Status of symptom
- Intensity
- Date of birth
- Demographic data
- Prior and concurrent medications
- Medical history and concurrent diseases
- Results of baseline tests: physical examination; vital signs; lab tests
- Questionnaire scores.

Personal data (including contact information) will be collected with the subject's permission and only to the extent that is necessary for the purposes of the study.

Exceptions to data collection:

- As androgen deprivation therapy (ADT) is given as part of standard of care, adverse events/toxicities that occur related to ADT will not be collected or reported.

The following data will be collected and evaluated according to the Study Calendar (Section 3.3):

- Physical examination
- Concomitant medications
- AEs
- Use of ADT
- Presence or absence of biochemical relapse
- Questionnaire scores

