8.4.3 Analysis of the Secondary Endpoint(s)

- Define the toxicity profile of image-guided, focally dose escalated prostate bed radiation in patients with a local or regional recurrence of prostate cancer after prostatectomy. All AEs except grade 1 with attribution to protocol treatment will be collected in tabulated way and analyzed.
- The rate of PSA control (biochemical progression free survival, bPFS) will be estimated by the Kaplan-Meier survival analysis and effects of clinical variables on bPFS will be assessed by the Cox proportional hazards model.
- The quality of life scores will be summarized at baseline and for each visit. Linear mixed effects model will be used to model quality of life scores at baseline and during and after treatment in which random intercept and random slope are used to account for patient-specific trajectory of quality of life scores. Changes of quality of life scores during and after treatment will be calculated from the estimated linear mixed effect model. The

similar analytical approach will be performed for depression scores and correlated with quality of life scores.

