8.4.4 Safety Analyses

Adverse events will be coded as per the CTCAE v4.0. Each AE will be coded once for each patient based on the maximum severity during the assessment period. The relationship of AEs to study intervention will be recorded in addition to the onset date, end date, severity, expectedness, and outcome.

Dose-limiting toxicities are defined as follows (during treatment and within the first three weeks after treatment):

- Grade 3 rectal, small bowel, or urinary toxicity that does not resolve to Grade 2 or less within 4 days with medical management
- Other grade 3 in-field toxicities attributable to radiation that do not resolve to Grade 2 or less within 4 days with medical management
- Delays of more than one week in completing radiation treatment due to toxicity (cumulative duration of delay over the course of the entire treatment).

Additionally, toxicities attributable to radiation after the DLT assessment period (3 weeks after radiation is completed) will be followed and scored but will not be used for escalation with the following exception. If Grade ≥ 4 late bowel or bladder injury (late toxicity is defined as occurring >90 days after completion of radiotherapy) is observed in 2 patients in any Dose level group, dose escalation will be terminated and the dose below that dose level in which the toxicity was observed will be considered the MTD. Early and late toxicities used for assessment of DLTs should be attributable (possible, probable or definite) to radiation. Sexual and erectile dysfunction as a result of radiation will not be considered a DLT. Note that MTD will be determined for each Group separately.

Dose-limiting toxicities are defined as per section **3.1.1**.

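### Section 6.1 makes recording of non-serious adverse events optional after day 30, although other sections require late toxicity to be scored to month 24

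*Combined protocol and SAP*

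**What the plan says.** Section 6.1 (Data Collection) gives two recording rules. The first is "Document AEs from the first study intervention through at least 30 days after the last study treatment administration". The second applies after that point, when "only adverse events which are serious and related to the study intervention need to be recorded". An event that has already begun is followed until it returns to baseline or stabilizes.

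Other sections set a wider scope for the same period:

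- Section 3.1.1: "toxicities that occur more than 3 weeks after completion of treatment and during the 24 month follow up period will be followed and scored".
- Section 8.4.4: "toxicities attributable to radiation after the DLT assessment period (3 weeks after radiation is completed) will be followed and scored". No end month is given. The same section states that "late toxicity is defined as occurring >90 days after completion of radiotherapy".
- Section 6.1.1 lists AEs under the heading "The following data will be collected and evaluated according to the Study Calendar". In section 3.3 the "Adverse Events" row is marked at baseline, during treatment, and at months 1, 3, 6, 9, 12, 15, 18, 21 and 24. No footnote on the row limits it to serious or related events.
- Section 8.4.3, on the toxicity profile: "All AEs except grade 1 with attribution to protocol treatment will be collected in tabulated way and analyzed". No time limit is stated.

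**The concern.** The data-collection section makes optional what the toxicity and analysis sections treat as required. Staff who follow 6.1 to the letter comply with it and can still leave the 8.4.3 table without its late inputs. Optional recording may also differ between patients and dose levels.

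The events exposed are new-onset, non-serious toxicities of Grade 2 or 3 after day 30. They matter in this trial for three reasons. Safety and tolerability is the first secondary objective (1.1.2). The Précis presents the accelerated schedule as one meant to keep late toxicity near its usual rate. Section 9.3.2.1 names lower-grade chronic bowel and bladder effects as a moderate risk. If such events are under-recorded, the late profile will look better than it is when read beside the background rates in 1.2.1.

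**Working it through.** The plan gives no figure to reproduce on this point. The check sets the rules side by side and then measures the period and the kind of event affected.

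**1. The rules compared**

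| Section | Period | Which events |
|---|---|---|
| 6.1, first rule | to at least day 30 | all AEs |
| 6.1, second rule | after that | serious and related only, as a minimum |
| 3.1.1 | after week 3 to month 24 | toxicities, no seriousness filter |
| 8.4.4 | after week 3, no end stated | radiation-attributable, no seriousness filter |
| 6.1.1 with 3.3 | to month 24 | AEs, no filter |
| 8.4.3 | no limit stated | AEs except Grade 1, no seriousness filter |

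A non-serious Grade 2 event that starts at month 12 and is attributed to radiation must be scored under 3.1.1 and 8.4.4 and tabulated under 8.4.3. Under 6.1 it need not be recorded.

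**2. Time under the reduced rule**

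Days are counted from the end of radiation, with 24 months taken as 730 days.

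- Period scored under 3.1.1: 730 − 21 = 709 days.
- Full recording required by 6.1 within it: days 22 to 30 = 9 days; 9/709 = 1.3%.
- Reduced rule: 730 − 30 = 700 days; 700/709 = 98.7%.
- Late period (beyond 90 days): 730 − 90 = 640 days, all under the reduced rule. The other 700 − 640 = 60 days are days 31 to 90, which 1.2.1 still classes as acute.
- Scheduled AE assessments under the reduced rule: months 3, 6, 9, 12, 15, 18, 21 and 24 = 8. The month 1 visit, with its window of one week either way (about days 23 to 37), can fall on either side of day 30.

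**3. Kind of event, for scale only**

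Section 1.2.1 gives late Grade 2 or higher rates of 25% (GU) and 18% (GI), and late Grade 3 or higher rates of 7% and 2%. The maximum sample size is 48 (8.2).

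- Grade 2 alone: GU 25 − 7 = 18%; GI 18 − 2 = 16%.
- Share of late Grade 2 or higher: GU 18/25 = 72%; GI 16/18 = 89%.
- Patients out of 48: GU 48 × 0.18 = 8.6; GI 48 × 0.16 = 7.7. These cannot be added, because one patient may have both.
- In a dose level of six, the chance of at least one patient with late Grade 2 toxicity only: GU 1 − 0.82^6 = 0.70; GI 1 − 0.84^6 = 0.65.

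The documents do not say what share of Grade 3 or higher events is serious. Assume that all Grade 2 events are non-serious and vary that share from 100% to 0%. The part of late Grade 2 or higher toxicity that 6.1 does not require to be recorded then runs from 72% to 100% for GU (8.6 to 12.0 of 48) and from 89% to 100% for GI (7.7 to 8.6 of 48).

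**The case against.** The strongest reply is that 6.1 only sets a floor. Both of its phrases are minimums, while 3.1.1 and 8.4.4 are specific and mandatory. A team that scores late toxicity under 3.1.1 breaches nothing in 6.1, and harm arises only if 6.1 is applied alone. It can be added that the calendar says when AEs are asked about, not which must be recorded, and that footnote 7 names adverse events as a purpose of the three-monthly remote contact. This is correct as far as it goes, and it is why the word is optional and not forbidden. It does not settle the matter: 6.1 is the section that governs recording, it differs from its own subsection 6.1.1, and nothing says which rule prevails.

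The wording of 8.4.3 can be read in two ways, since the attribution phrase may qualify all AEs or only Grade 1. On either reading, non-serious attributable events of Grade 2 and above are to be tabulated.

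The questionnaires (EPIC-26, AUA-SI) capture some late urinary and bowel symptoms. They are six-monthly, for English speakers only, and do not give the CTCAE grades that 8.4.4 uses.

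The limits on consequence stand. DLTs occur inside the full-recording window. Grade 4 or higher late injury, which can stop escalation, would ordinarily be serious and so recorded. Events that start by day 30 are still followed. No formal test against the background rates is planned.

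**Conclusion.** The concern holds. The recording rule in 6.1 is narrower than the late-toxicity scope in 3.1.1, 8.4.4, 6.1.1 and the Study Calendar, and narrower than the analysis in 8.4.3. About 99% of the post-DLT scoring period, all of the late period and all eight assessments from month 3 onward lie under the reduced minimum. The determination of the MTD is essentially untouched. What is exposed is the completeness of a descriptive secondary result, and any loss would make it look favourable. This should be fixed, but it does not threaten the primary objective.

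The time figures rest on 730 days of follow-up; patients taken off study earlier, for example at recurrence (3.7.2), contribute less. The patient counts are not an estimate of lost data. They assume that all 48 are treated, although 8.2 calls that number a likely over-estimate, and that the 1.2.1 rates apply over 24 months, although no time horizon is given for them.

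**What to change.** Amend 6.1 so that every AE of Grade 2 or higher that is possibly, probably or definitely attributable to radiation is recorded through month 24, whether or not it is serious. Add no in-field restriction, so that 6.1 supplies what 8.4.3 is to tabulate. Leave the present reduced requirement in place only for Grade 1 and non-attributable events; as now, 6.1 would then require no recording of non-attributable events after day 30. State in 3.1.1 and 8.4.4 that this is the recording standard for late toxicity. A short pointer to 6.1 from 6.1.1 and the AE row of the calendar would close the remaining difference in scope. The exception in 6.1.1 for ADT-related events can stay.

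The cost is wording in these sections and modest extra data entry. No visits are added: AE assessment is already scheduled at each follow-up visit to month 24, with three-monthly remote contact for those who cannot attend.

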7. +/- 1 week for 1 month visit, +/- 2 weeks for 3 and 6 month visits. +/- 4 weeks for next visits. If subjects are not able or willing to come to NIH to FU visits, they will be followed every three months remotely (by phone call, e-mail for adverse events or other NIH approved remote communication platform), further tumor therapy and lab results. Lab results from outside laboratories are accepted. A clinical evaluation may be completed remotely with a member of the study team to determine if the physical exam, vital signs and ECOG may be omitted. A subject may be referred to a local providers for further assessment at the discretion of the investigator after a remote assessment (e.g., finding that requires clinical assessment/follow up). Subjects may also be referred to their local provider for labs. If biochemical failure per **6.3.1** is identified, the second measurement will be obtained for confirmation, ideally at the NIH Clinical Center. Imaging may be delayed, but will be completed as soon as feasible. Collection of research blood or urine will be omitted or collected in a delayed fashion.
8. Only at the 6 month follow up time point.
9. Scans may be omitted if eligibility can be determined from MRI or other imaging results including 18F-DCFPyL.

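### Section 6.1's recording minimum after day 30 is narrower than the late-toxicity follow-up required elsewhere, so non-serious late Grade 2–3 events could go unrecorded

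*Combined protocol and SAP*

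**What the plan says.** Section 6.1 sets two recording periods. Adverse events are documented from the first intervention "through at least 30 days after the last study treatment administration". After that, "only adverse events which are serious and related to the study intervention need to be recorded". The same section says that adverse events, "regardless of severity, will be followed until return to baseline or stabilization of event".

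Other parts of the document describe wider collection:

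- Section 3.1.1: "toxicities that occur more than 3 weeks after completion of treatment and during the 24 month follow up period will be followed and scored". Section 8.4.4 says much the same for radiation-attributable toxicity after the DLT period, and defines late toxicity as starting more than 90 days after radiotherapy.
- Section 6.1.1 lists adverse events among the items under "The following data will be collected and evaluated according to the Study Calendar (Section 3.3"). The "Adverse Events" row of that calendar is marked at every follow-up visit to month 24. Footnote 7 covers patients who cannot attend: "they will be followed every three months remotely (by phone call, e-mail for adverse events or other NIH approved remote communication platform"). The one exception that Section 6.1.1 names is that "adverse events/toxicities that occur related to ADT will not be collected or reported".
- Section 8.4.3 plans to collect, tabulate and analyze every treatment-attributed adverse event above Grade 1.

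None of these limits late events to serious ones, and no text says which rule governs.

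**The concern.** The toxicity profile is a secondary objective (Sections 1.1.2 and 8.1.2), and the précis describes the accelerated treatment as designed to give a late-toxicity rate similar to that of standard treatment. By the Section 8.4.4 definition, every late event falls in the period where Section 6.1 asks only for serious, related events. A new Grade 2 or Grade 3 bowel or bladder event that is not serious could be seen at a scheduled visit and still not be entered.

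The resulting error has one direction: omission can only lower the apparent rate of late toxicity. Recording might also differ between staff or dose levels, depending on which section is followed. Nothing else in the plan fills the gap. Late Grade 3 toxicity plays no part in the MTD rule, so adverse event records are the only CTCAE-graded evidence on it. The six-monthly questionnaires cover urinary and bowel symptoms, but only for English speakers and without a CTCAE grade.

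**Working it through.** **1. The texts side by side**

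| Source | Period | Filter on events |
|---|---|---|
| 6.1 | beyond 30 days | serious and related |
| 3.1.1 / 8.4.4 | from 3 weeks after treatment, to 24 months in 3.1.1 | no seriousness filter; 8.4.4 requires attribution to radiation |
| 6.1.1 with 3.3 | every visit to month 24 | none, apart from ADT toxicity |
| 8.4.3 | none stated | attributed to treatment, above Grade 1 |

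These are three independent sources against Section 6.1. Section 8.4.4 largely repeats 3.1.1, and Section 6.1.1 points to the 3.3 calendar.

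**2. What falls in the gap**

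- DLT window: treatment plus 3 weeks, so it ends on day 21, inside the 30 days of full recording. Not affected.
- Events that begin by day 30: recorded, then followed to resolution or stabilization. Not affected.
- New non-serious events from day 31 to day 90: need not be recorded under 6.1.
- New non-serious events after day 90, meaning all non-serious late toxicity: need not be recorded under 6.1.
- Scheduled visits after day 30 with adverse events marked: months 3, 6, 9, 12, 15, 18, 21 and 24, eight in all.
- Late Grade 4 or higher bowel or bladder injury (the stopping exception): still recorded if it counts as serious.

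**3. Number of patients**

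The plan's maximum reproduces: 3 dose levels × 6 patients + 6 in expansion = 24 per arm, and 2 × 24 = 48 (Section 8.2).

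**4. Expected late events in a full arm of 24**

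Rates are those in Section 1.2.1. Grade 2 only is Grade 2 or higher minus Grade 3 or higher: GU 25% − 7% = 18%, GI 18% − 2% = 16%. Expected patients = 24 × rate.

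| | Grade ≥2 | Grade ≥3 | Grade 2 only |
|---|---|---|---|
| GU | 24 × 0.25 = 6.0 | 24 × 0.07 = 1.7 | 24 × 0.18 = 4.3 |
| GI | 24 × 0.18 = 4.3 | 24 × 0.02 = 0.5 | 24 × 0.16 = 3.8 |

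Grade 2 only therefore makes up 18/25 = 72% of the GU patients and 16/18 = 89% of the GI patients.

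**5. How many would be recorded if staff kept to the 6.1 minimum**

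The documents do not give the share of late events that are serious. For illustration only, assume that 0–25% of Grade 2 and 25–100% of Grade 3 or higher events are serious. Recorded rate = s2 × Grade 2 only + s3 × Grade ≥3.

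- GU: low 0 × 0.18 + 0.25 × 0.07 = 0.0175; high 0.25 × 0.18 + 1 × 0.07 = 0.115. In 24 patients, 0.4 to 2.8 recorded of 6.0.
- GI: low 0 × 0.16 + 0.25 × 0.02 = 0.005; high 0.25 × 0.16 + 1 × 0.02 = 0.06. In 24 patients, 0.1 to 1.4 recorded of 4.3.

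Without any assumption about seriousness, the recorded number could lie anywhere from none to all.

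**The case against.** The best defence is that Section 6.1 sets a floor. It says what needs to be recorded, its 30 days is itself a minimum, and it forbids nothing. Recording every attributable late event above Grade 1 would satisfy 6.1, 3.1.1, 8.4.4 and 8.4.3 together, so the wider duty already exists and what is missing is a carve-out in 6.1. That is right as far as it goes. A reader might infer that staff who stop at the 6.1 minimum comply with the protocol. They would not: they would meet 6.1 and fall short of 3.1.1 and 8.4.3. But the general data-collection section is a natural place for staff to look for the recording rule, and it does not point to the wider one.

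Some of the supporting text is also weaker than it looks. A calendar mark or a remote contact shows that adverse events are assessed, which is needed to detect serious ones too. Section 8.4.3 gives no time window. The clearest conflict is therefore 3.1.1 and 8.4.4 against 6.1.

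The promise in 6.1 to follow events whatever their severity does not close the gap. It concerns follow-up and does not require recording of a new non-serious event that starts after day 30.

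Finally, the plan has no formal comparison of late toxicity with published rates; the only stated comparison with published series is for bPFS (Section 8.1.2). That limits the harm to a descriptive profile, but an incomplete descriptive profile still misinforms.

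**Conclusion.** The inconsistency is real and unreconciled. New-onset, non-serious Grade 2–3 radiation toxicity after day 30 could go unrecorded, and the secondary toxicity profile could be biased toward lower late toxicity. It is worth correcting, because the omission affects the events on which the late-tolerability description depends.

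The documents do not support two stronger readings. One is that late events will be lost: 6.1 permits the omission but does not order it. The other is that the MTD is compromised: DLTs are assessed inside the full-recording period, and the late Grade 4 or higher stop is intact provided such injuries count as serious.

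The size is illustrative. About 6 GU and 4 GI patients with late Grade 2 or higher toxicity in an arm of 24 assumes that the Section 1.2.1 rates apply here. That section gives no follow-up time for them, so 24-month rates may be lower. It also assumes the arm reaches its maximum, which Section 8.2 calls a likely overestimate, and it pools three dose levels. The recorded ranges add assumed serious shares and staff who record only the minimum. The conflict between the sections depends on none of these figures.

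**What to change.** Replace the Section 6.1 sentence on events beyond 30 days with:

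> Beyond 30 days and through 24 months after the last treatment, all Grade ≥2 adverse events attributable (possible, probable or definite) to radiation are recorded, whether or not serious.

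Keep the ADT exception in Section 6.1.1. In Section 8.4.3, have the planned tabulation show late (more than 90 days) bowel and bladder events by arm and dose level. Escalation and stopping rules stay as they are.

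The cost is small. Adverse events are already assessed at every calendar visit to month 24, so no patients or visits are added. The downsides are slightly more late recording and a chart review for patients already more than 30 days past treatment.
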